Electrocardiogram (ECG) ²	Х	X (predose AND 2h postdose) ³	х	X (predose AND 2h postdose) ³	Х	x	Х	X³	x	x
Vital Signs	Х	Х	Х	Х	Х	Х	Х	Х	Х	Х
Body Height	Х									
Body Weight	Х	Х		Х		Х	Х	Х	Х	
Hepatitis screen, HIV screen	Х									
Hematology, Clinical Chemistry, Urinalysis	х	х	х	х	Х	х	х	х	х	Х
	1									
Pregnancy Test (Serum)	Х	Х		Х		Х	Х	Х	Х	
Pregnancy Test (Urine)		S								
	8									
Concomitant medications/ Surgical or Medical Procedure	Х	х	Х	X	Х	x	x	Х	x	x
Adverse Events	Х	Х	Х	Х	Х	X	Х	Х	Х	Х

Table 6-1Assessment Schedule

Period	Screening	ening Treatment Follow-up (EOS/PSW)							Unplanned	
Visit Day	-28 to -1	1	15	29	43	57	85	113 ¹	141	-
Weeks	-4 to -1	0	2	4	6	8	12	16	20	0
Patient e-Diary daily entry ⁴					Х					
Patient e-Diary Review		Х	Х	Х	Х	Х	Х	Х	Х	Х
IGA, EASI (incl. BSA),	х	х	x	x	х	x	х	х	x	х
Drug dispensation ⁵		Х		Х		Х	Х			
Drug accountability				Х		Х	Х	Х		
Dosing at site ⁶		Х	Х	Х	Х	Х	Х			
Study Disposition	X									

¹Visit must be the day after the last day of dosing i.e. Day 113; End of treatment visit (EOT) or treatment discontinuation (TD)

²All ECGs are to be performed under fasted conditions (subjects should fast at least 3 hours before the site visit and remain fasted until the last ECG is done). ECG should be done after 10 min rest in supine position, followed by vital signs while supine and then blood samples

³Triplicate standard 12-lead ECGs will be performed at: Baseline (triplicate before intake of drug and triplicate 2 hours post dose), Week 4 (triplicate before intake of drug and triplicate 2 hours post dose), and at Week 16 (triplicate before intake of drug). Single standard ECGs should be done at all other visits.

⁴Starting 1 week prior to Baseline. The investigational site staff must make a phone call to the patient to remind them to switch on the device and start completion. Patient e-Diary will include daily use of emollients, study drug and rescue therapy (if any).

⁵Subjects should be instructed to take study medication every day at the same time preferably in the morning except on study visit days. The subject will record the intake of study medication on a daily basis on the subject e-diary.

⁶ On days of a study visit, subjects should not take the investigational treatment at home; instead they will take it when instructed by study personnel at the investigational site

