# 2.1.1 General definitions

Study treatment is either placebo or 3, 10, 30 or 50mg ZPL389.

Day 1 is defined to be the first day of administration of any study treatment.

All other study days will be labeled relative to Day 1. For event dates on or after Day 1, studyday for a particular event date is calculated as [Date of event] – [Date of first dose]+1, i.e., Day 2, Day 3, etc., will be one day, two days, etc., after Day 1, respectively. For the dates beforeDay 1, study day for an event date is calculated as [Date of event] – [Date of first dose], i.e., Day - 1, Day -2, etc., will be one day, two days, etc., before Day 1, respectively. Duration of an event will be calculated as (Event end date – Event start date + 1).

The descriptor "Day 0" will not be used.

Screening refers to any procedure (e.g., checking inclusion and exclusion criteria) performed prior to the date of first dose of study treatment. Per protocol, subject informed consent must be obtained prior to performing any study related activity. The date of signing informed consent is the start date of screening period.

Baseline is considered to be the last assessment (including those from unscheduled visits) obtained before the first dose of study treatment. All assessments obtained after first dose of study treatment are considered as post-baseline unless otherwise specified.

In general, a baseline value refers to the last measurement made prior to administration of the first dose of study treatment. However, if no pre-treatment value exists, values obtained after first dose of treatment but on that same day of dosing will be considered as the baseline.

The date of last dose will be collected via the CRF. The end of the treatment period will be defined as the last dose date or last visit in treatment period whichever occurs earlier. i.e., for subjects who discontinued or have their last visit earlier than last dose date, the end of study treatment will be the date of the last study visit in the corresponding treatment period.

The core study treatment period is defined to be the time up until the date of the first visit in the extension study whilst the patient is receiving study treatment.

The extension study treatment period is defined to be the time up from the first visit in the extension study until the end of study treatment

The follow-up period is defined to be the time from last dose of study treatment until the end of the study (latest of core and extension for that patient).

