
The concept of assessment windows will be used for the data that is summarized by visit. Each assessment window is based on the study evaluation schedule and comprises a set of days around the nominal visit day. For any assessment, there are the protocol defined scheduled visits around which windows were created to cover the complete range of days within the study. The visit windows are shown in Table 2-1.

These assessment windows apply to measurements taken at every visit. For assessments which are not collected at every visit, the assessment windows defined in Table 2-1 will be combined. For example, if an assessment is measured at Week 4 and Week 8 only, the Week 4 assessment window for this parameter will extend from Day 2 to Day 43 (combining Week 2 to Week 4), Week 8 will extend from Day 44 to Day 71 (combining Week 6 to Week 8).

When assessment windows are used, all visits will be re-aligned, i.e., they will be mapped into one of the assessment windows. For example, if the Week 4 visit of a subject is delayed and occurs on Day 60 instead of on Day 29, the data will be considered to relate to Week 8. In the case of major deviations from the visit schedule, or due to unscheduled visits, several assessments of a subject may fall in a particular assessment window (either scheduled or unscheduled). The approaches to handle multiple assessments in a given window are specified below.

Assignment of data to the assessment windows will be done before deriving further parameters (e.g. change from baseline, responder status) from the assessments. The assessment windows will be used for summary tables and figures but listings will show the original visit at which the data were recorded, along with the study day of the assessment.

I able 2-1			
Visit as used for reporting	Week	Scheduled study day	Assessment window
Screening	SCN	-35 to -1	Day -35 to -1
Baseline	0	1	Day 1
Week 2	2	15	Day 2 – 22
Week 4	4	29	Day 23 – 26
Week 6	6	43	Day 37 – 50
Week 8	8	57	Day 51 – 71
Week 12	12	85	Day 72 – 99
Week 16	16	113	Day 100 – 127
Week 20	20	141	Day 128 – 155
Week 28	28	197	Day 184-211
Week 32	32	225	Day 212-267
Week 44	44	309	Day 268-351
Week 56	56	393	Day 352-435
Week 68	68	477	Day 436-519
Week 80	80	561	Day 520-603
Week 92	92	645	Day 604-687

Table 2-1Visit windows

Novartis For business use only SAP		Page 15 CZPL389A2203	
Visit as used for reporting	Week	Scheduled study day	Assessment window
Week 104	104	729	Day 688-771
Week 116	116	8130	Day 772-827

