Week 120	120	841	Dav >= 828

If more than one assessment falls into the interval, the rules defined below will be applied unless otherwise specified.

- for quantitative variables, the closest to the actual visit is chosen (if two assessments have the same distance, then the earlier one will be chosen);
- for qualitative variables, the worst record is selected.

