# 2.7.1.1 Adverse events of special interest / grouping of AEs

Summary tables showing the effects of ZPL389 in the core study on QTc and liver events will be produced following standard tables.

Additionally since part of the study was conducted during the COVID-19 pandemic, a listing of patients with suspected or confirmed SARS-COV-2 infection will be produced.

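### The SAP gives no visible rule for triplicate and 2-hour post-dose ECGs; if its default window rules are applied to QTc, no post-dose value enters a windowed summary and each triplicate shrinks to one tracing

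*SAP*

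**What the plan says.** **ECG schedule (Protocol Table 6-1, footnote 3).** Triplicates are taken before and 2 hours after dosing at Baseline and again at "Week 4 (triplicate before intake of drug and triplicate 2 hours post dose". A further triplicate is taken at Week 16, and single ECGs at all other visits. The Day 1 and Week 4 post-dose sets are the only ECGs that the protocol times after a dose.

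**Baseline (SAP 2.1.1).** "In general, a baseline value refers to the last measurement made prior to administration of the first dose of study treatment". Values obtained after the first dose count as post-baseline unless otherwise specified.

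**Windows (SAP 2.1.1 and Table 2-1).** "The concept of assessment windows will be used for the data that is summarized by visit". Day 1 belongs only to the Baseline window, and the first post-baseline window (Week 2) starts on Day 2. The Week 4 window is printed as Day 23 to 26 although the scheduled day is 29, and the Week 6 window starts on Day 37. Values are assigned to windows before change from baseline or other parameters are derived.

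**Several values in one window (SAP 2.1.1).** "the rules defined below will be applied unless otherwise specified". For quantitative variables the value closest to the visit is kept, and "if two assessments have the same distance, then the earlier one will be chosen". By contrast, "for qualitative variables, the worst record is selected".

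**Planned QTc output.** SAP 2.7.1.1: "Summary tables showing the effects of ZPL389 in the core study on QTc and liver events will be produced following standard tables". Protocol 9.5.2 promises ECG summary statistics, shifts against normal ranges and counts of notable abnormalities. Neither place says that the summaries are by visit.

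**The concern.** QT prolongation is the cardiac risk that the protocol names. Protocol 3.6 reports clinically relevant QTcF increases at single doses of 300 and 400 mg, at concentrations above the steady-state peak of 50 mg once daily. It also reports that the concentration-QTcF analysis of the 50 mg regimen gave no result of regulatory concern. Amendment 2 moved the post-dose ECG from 0.5 to 2 hours after Phase I results, so the time point was chosen deliberately.

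A one-record-per-window rule suits a visit with one planned measurement. It does not suit a visit with six planned tracings at two time points. If it is used for QTcF, the tables would omit the measurements timed to show a post-dose effect. They would also give up the precision that triplicates were scheduled to provide, including in the baseline from which every change is calculated.

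**Working it through.** The plan states no figure to reproduce. The check applies the written rules to the scheduled tracings.

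**1. Scheduled core-study tracings per completer (Protocol Table 6-1).** Screening 1, Baseline 6, Week 2 1, Week 4 6, Weeks 6, 8 and 12 one each, Week 16 3, Week 20 1. Total 1 + 6 + 1 + 6 + 3 + 3 + 1 = 21, of which 3 + 3 = 6 are post-dose.

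**2. Rules applied.** Distance is counted in study days (an assumption; visits have no nominal clock time). One record is kept per window, and ties go to the earlier.

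| Week 4 window | Tracings kept | Post-dose kept | What happens at Week 4 |
|---|---|---|---|
| As printed, Day 23 to 26 | 8 of 21 | 0 of 6 | All six Day 29 tracings fall in no window |
| Contiguous, Day 23 to 36 (assumed correction) | 9 of 21 | 0 of 6 | One pre-dose tracing kept by the tie rule |

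On Day 1 the baseline definition selects the last pre-dose tracing, whereas the tie rule would select the first. Both leave out the post-dose set, and no post-baseline window contains Day 1. At Week 16 one of three tracings is kept.

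**3. Pre-dose against post-dose exposure.** Protocol 3.3 gives a terminal half-life of 70 to 100 hours. Assume one compartment, rapid absorption and an effect linear in concentration. By Day 29, 28 × 24 = 672 hours have passed, or 6.7 to 9.6 half-lives, which is essentially steady state.
- Peak at dosing: trough/peak = 2^(−24/70) = 0.788 to 2^(−24/100) = 0.847, a gap of 15 to 21%.
- Peak at 2 hours, so 22 hours to the next pre-dose ECG: 2^(−22/70) = 0.804 to 2^(−22/100) = 0.859, a gap of 14 to 20%.

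Pre-dose values alone would therefore understate a linear peak effect by about 14 to 21%. Within this model that is near an upper limit, because slower absorption flattens the curve.

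**4. Weight of the Day 1 set.** In the same model accumulation is 1/(1 − 0.788) = 4.7 to 1/(1 − 0.847) = 6.5. The steady-state trough is then about 3.7 to 5.5 times the first-dose peak (accumulation × trough/peak). Later pre-dose ECGs carry more exposure than the Day 1 post-dose set, so the Week 4 set is the more informative of the two.

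**5. Loss of precision.** The documents give no ECG variance components. Assume a day-to-day SD of 6 to 10 ms and a replicate SD of 5 to 10 ms.
- Triplicates at both time points (Weeks 4 and 16): variance of change with single tracings relative to triplicate means = (σd² + σr²)/(σd² + σr²/3). Lowest: (100 + 25)/(100 + 8.33) = 1.15. Highest: (36 + 100)/(36 + 33.3) = 1.96.
- Single ECG at the visit, only baseline averaged (Weeks 2, 6, 8, 12, 20): (σd² + σr²)/(σd² + 2σr²/3). Lowest: 125/116.7 = 1.07. Highest: 136/102.7 = 1.32.

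**The case against.** The strongest reply is that nothing visible says the default rule will be used on these data.

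- **Hidden section.** The rule yields to any other specification. The SAP contents list 2.7.4, on other safety data, but its text is not available. An ECG rule there would settle the matter. This stands, and makes the finding conditional.
- **No by-visit commitment.** Windows apply to data summarised by visit, and neither document promises QTc by visit. This also stands. The visible text would still not say which of six same-day values enters a QTcF summary.
- **Purpose of the rule.** It is introduced with the words "In the case of major deviations from the visit schedule, or due to unscheduled visits, several assessments of a subject may fall", which points away from planned replicates. This stands in part: the same passage covers scheduled as well as unscheduled assessments, and the rule is triggered whenever a window holds more than one.
- **Other readings.** A triplicate could count as one assessment. A post-dose ECG could count as an assessment not made at every visit, with combined windows that would reach Day 29. Both are possible, but the visible text says neither, and the second needs the separate time point that the SAP does not define.
- **Other protection.** Categorical results take the worst record, and listings show the original visit. ECGs are read centrally (Protocol 6.5.3). Notable QTcF values, including a 30 msec increase from Baseline, are flagged for the investigator (Protocol 7.5). All of this stands. It protects patients but does not supply the missing rule for mean QTcF and its change from baseline.

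**Conclusion.** The gap is real. If QTc is summarised by window and SAP 2.7.4 contains no ECG rule, 0 of 6 scheduled post-dose tracings enter a windowed post-baseline summary, and each triplicate contributes one tracing. The route differs: on Day 1 the baseline and window definitions, at Week 4 the printed window or, once that is corrected, the tie rule.

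A reader might infer three stronger things that the documents do not support.
- That the post-dose ECGs are certain to be dropped. The two conditions above are open.
- That the tables will show trough values and understate the QTc effect by at least 15 to 21%. The figure is about 14 to 21%, near an upper limit under a one-compartment, linear model. The single ECGs at Weeks 2, 6, 8 and 12 are not timed relative to the dose taken at site, so they cannot be called troughs. The variance ratio of 1.15 to 1.96 rests on assumed SDs and holds only where both time points are triplicates.
- That patient safety depends on this rule. Central reading and flagging work independently of it.

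The SAP also serves an abbreviated report of studies stopped for lack of efficacy. This is a minor to moderate improvement, worth making because it is almost free, and not a condition for accepting the analysis.

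**What to change.** Add an ECG paragraph to SAP 2.1.1, or a cross-reference if 2.7.4 already covers it:
- Triplicate ECGs are averaged within each time point before any window selection.
- QTcF baseline is the mean of the Day 1 pre-dose triplicate.
- Pre-dose and 2-hour post-dose at Day 1 and at Week 4 are separate analysis time points, each summarised as change from baseline by dose. The Day 1 post-dose set is post-baseline even though it falls on Day 1.
- The one-record rule applies within a time point, to repeat or off-schedule visits only.

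In Table 2-1, reconcile the Week 4 window with Day 29. Day 23 to 36 would be contiguous with the Week 2 and Week 6 windows. In 2.7.1.1, say whether QTc tables are by visit and time point.

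The cost is SAP wording, one time-point variable and an averaging step. The ECGs are already in the schedule, so no new data are needed.

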# **Confounding medications**

Any use of rescue medication or prohibited medication will be considerd as confounding therapy, where rescue medications are collected from the rescue therapy CRF and concomitant medications listed below will be considered as prohibited medications.

- 1. All cases of conmeds in the following ATC classes
  - D07 CORTICOSTEROIDS, DERMATOLOGICAL PREPARATIONS
  - R06A ANTIHISTAMINES for systemic use
- 2. Conmeds in the class L04 IMMUNOSUPPRESSANTS that are also PDs with PD identifier COMD3.

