5.5.8 Prohibited medication

Use of the treatments displayed in the below table is NOT allowed during the period specified below in Table 5-1.

Medication/therapy	Prohibited period	Action taken
Tapical corticostoroids (TCS)	a) Within 1 week prior to Baseline	a) Delay randomization to achieve 1-week wash out or discontinue subject from trial
Topical controsteroids (TCS) Topical calcineurin inhibitors (TCI) Other topical treatment for AD such as crisaborole, tar etc. Initiation of treatment of AD with prescription moisturizers or moisturizers containing ingredients such as ceramides, lactic acid, urea, α -hydroxy- or fruit acids, vitamins A or D	b) Treatment period c) Follow up period	 b) Discontinue prohibited medication and continue study treatment OR If the subject meets criteria for rescue medication and only after 4 weeks post Baseline, follow instructions in Section 5.5.6** c) Discontinue prohibited medication, unless patient is in the follow up period after early treatment discontinue prohibited
Systemic immunosuppressive treatments* including but not limited to systemic corticosteroids (e.g., i.v., i.m. or oral), cyclosporine, tacrolimus, cyclophosphamide, azathioprine, methotrexate, mycophenolate mofetil, JAK inhibitors, apremilast, biologic therapies (like dupilumab, etanercept, adalimumab, infliximab, omalizumab), chinese traditional medicine	a) Within 4 weeks prior to Baseline for non biologics / within 3 months prior to Baseline for biologic treatments or within 5 half-lives of Baseline, whichever is longer	a) Discontinue subject from trial and rescreen subject after wash- out and if recruitment period is still ongoing

 Table 5-1
 Prohibited medication/therapy

Medication/therapy	Prohibited period	Action taken		
	b) Treatment period	b) Discontinue prohibited medication and continue study treatment unless there is a specific safety risk for the subject, in the opinion of the investigator in which case study treatment must be discontinued		
	c) Follow up period	c) Discontinue prohibited medication		
Oral antihistamines (H1 antihistamines are allowed if the subject is on a stable dose or used short term to, for example, treat allergies)	a) Within 1 week prior to Baseline	a) Delay randomization to achieve 1-week wash out or discontinue subject from trial		

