	b) Treatment period	b) Discontinue the prohibited therapy, and continue study treatment unless there is a specific safety risk for the subject, in the opinion of the investigator in which case study treatment must be discontinued		
	c) Follow up period	c) Discontinue prohibited medication		
Phototherapy or tanning booths Bleach baths	a) 4 weeks prior to Baseline	a) Discontinue subject from study and rescreen subject after wash- out if the recruitment period is still ongoing		
	b) Treatment period	 b) Discontinue prohibited medication/therapy, and continue study treatment 		
	c) Follow up period	c) Discontinue prohibited medication		
Any investigational treatment	a) Within 5 half-lives of Baseline or until the expected pharmacodynamic effect has disappeared, whichever is longer	a) Discontinue subject from trial and rescreen subject after wash- out if the recruitment period is still ongoing		
	b)Treatment period	b) Discontinue subject from study treatment		
	c) Follow up period	c) Discontinue prohibited medication		
Any drug known to prolong QTc interval (See https://crediblemeds.org/ for details as well as protocol supplementary guidance) Drugs known to be hepatotoxic (please see protocol supplementary guidance) [#]	a) Within 5 half-lives of Baseline or until pharmacodynamic effect has disappeared, whichever is longer	 a) Discontinue subject from study and rescreen subject after wash- out if the recruitment period is still ongoing 		
	b) Treatment period	b) Discontinue study treatment		
Medication/therapy	Prohibited period	Action taken		
---	----------------------------------	---	--	--
Strong (Potent) CYP1A2 inhibitors (see protocol supplementary guidance) for all subjects	c) Follow up period	c) Discontinue prohibited medication (unless taken 4 weeks after early treatment discontinuation where it can be		
For subjects that are poor CYP2D6 metabolizers, strong and moderate CYP1A2 inhibitors (see protocol supplementary guidance)		allowed if medically necessary)		
Patients participating in must not	a) Within 2 weeks of Baseline	a) Patient is not eligible for substudy and will not participate		
take	b) Treatment period	b) Discontinue prohibited		
	c) Follow up period	treatment		
		c) Discontinue prohibited medication		

*CS nasal sprays and eye drops are not considered systemic immunosuppressive treatment

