# 2.3.2 Demographics and baseline characteristics

The demography and baseline characteristics summaries are intended to answer the questions:

- Is the trial population the one we intended to recruit?
- Are the characteristics of the trial population similar across treatment groups?

Contrary to the protocol, demographics and baseline characteristics will be summarized for the full analysis set instead of the randomized set. This will enable a comparison of the population for whom efficacy data is presented, with other studies.

Only key demographic and baseline characteristics that would be important to understand the patient population and put efficacy results into context of other trials will be presented.

Specifically these are:

- Age and age category (<65 years, 65 years and older)
- Weight
- Body mass index
- Gender
- Race
- Smoking status
- Baseline IGA score categories (moderate, severe)
- Baseline EASI

- Baseline total body surface area (BSA) affected by AD
- Time since diagnosis of AD
- Age at the time of diagnosis of AD
- Previous exposure to systemic corticosteroids(yes, no)
- Previous exposure to topical corticosteroids (TCS) therapy (yes, no)
- Previous exposure to topical calcineurin inhibitors (TCI) therapy (yes, no)
- Previous exposure immunosuppressant therapy for atopic dermatitis (yes, no)
- Previous exposure biologic systemic therapy for atopic dermatitis (yes, no)
- Previous exposure to other therapy for atopic dermatitis (including phototherapy and tanning booths) (yes, no)

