#### 2.4.2 **Prior**, concomitant and post therapies

The summaries of study treatment intake are intended to answer the question:

- What medications were used by patients before start of this trial?
- What medications were used by patients whilst on treatment in this trial?
- What medications were used by patients after study treatment in this trial

Other questions related to the intake of confounding treatment (treatment that may be considered to affect the efficacy outcomes) are considered in later sections.

This summary will be based on the safety set to include all patients who received study treatment according to the treatment they received.

Medications will be presented by ATC code and preferred term. ATC codes will be displayed in alphabetical order, and grouped by anatomical main group (the first level of the ATC code).

Medical procedures and significant non-drug therapies as coded in MedDRA will be summarized along with medications.

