# 2.5 Analysis of the primary objective

# 2.5.1 Primary endpoint

The primary objective for the extension study is to assess safety of ZPL389. This is described in section 2.8. This section focuses on the primary objective of the core study which is to characterize the dose-response relationship of ZPL389 in subjects with moderate to severe AD assessed by IGA response after 16 weeks of treatment.

The primary clinical question of interest is: What is the effect of ZPL389 versus placebo on IGA response after the full 16 weeks of treatment in patients with moderate or severe atopic dermatitis, who do not use confounding therapy that may affect their AD or the assessment of it, regardless of their use of protocol-allowed concomitant medicatons?

This estimand will enable assessment of the effect of ZPL389 in the absence of confounding medication (such as rescue medication) and after the intended 16 weeks of treatment.

The primary estimand is described by the following attributes:

**Population:** Adult moderate to severe atopic dermatitis patients as defined by the study inclusion and exclusion criteria who were randomized to treatment, and not mis-randomized in the IRT. This implies that analyses will be based on the full analysis set.

**Endpoint:** IGA response at week 16, where IGA response is defined as an IGA score of 0 or 1 with at least a 2 point improvement compared to baseline and no use of confounding therapy before the assessment time point.

**Treatment of interest:** the randomized treatment (ZPL389 or placebo) plus medications as allowed by the protocol but with no further treatment for patients who discontinue study treatment due an AE or lack of efficacy.

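### The SAP's list of confounding medications omits several AD treatments that the protocol prohibits, so some of their users can count as IGA responders

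*SAP*

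**What the plan says.** SAP 2.1.1, under Confounding medications, opens with a general rule: "Any use of rescue medication or prohibited medication will be considerd as confounding therapy". Rescue use is taken from the rescue therapy CRF. For everything else the rule narrows: "concomitant medications listed below will be considered as prohibited medications". The list holds all concomitant medications in D07 (dermatological corticosteroids) or R06A (systemic antihistamines), and L04 immunosuppressants only if they are also protocol deviations coded COMD3. There is no catch-all clause.

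This definition feeds the primary endpoint in SAP 2.5.1, where a responder must have had no confounding therapy before the assessment. The stated aim is: "This estimand will enable assessment of the effect of ZPL389 in the absence of confounding medication (such as rescue medication". The same section explains that all confounding use now counts as non-response, where the protocol counted only adjudicated use. Section 4 repeats that adjudication will not be done.

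Protocol Table 5-1 (5.5.8) has a wider reach during the treatment period. Its topical row covers TCS, TCI and "Other topical treatment for AD such as crisaborole, tar etc". Its systemic immunosuppressive row is open-ended, "including but not limited to systemic corticosteroids (e.g., i.v., i.m. or oral" and others. A further row reads "Phototherapy or tanning booths Bleach baths".

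**The concern.** The SAP replaces case-by-case judgement with a fixed list, and the list is shorter than the protocol's table of prohibited treatments. A patient whose skin was cleared by an unlisted treatment would be credited to the randomized arm as an IGA response. The estimand is meant to exclude that. The SAP presents the change as a broadening, from adjudicated use to any use. For drugs that adjudication could have judged confounding but that are not on the list, it is a narrowing, and section 4 does not disclose this.

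The list also governs EASI50 and EASI75 response (SAP 2.6.1 and 2.6.5). In SAP 2.6.2 it decides which EASI values are set to missing after confounding use, so values recorded after an unlisted therapy stay in that analysis unless treatment was also discontinued.

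**Working it through.** There is no figure in the plan to reproduce on this point. The check compares the two texts, follows one patient through the rules, and ends with simple arithmetic.

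**Step 1. Table 5-1 against the SAP list**

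| Prohibited in Table 5-1 | Reached by the SAP rule? | Basis |
|---|---|---|
| TCS | Yes | D07, or the rescue CRF |
| Oral antihistamines | Yes, and more widely than prohibited | All R06A, although the protocol allows H1 antihistamines at a stable dose or short term |
| Phototherapy, tanning booths | No | The list holds medications by ATC class; these are not drugs |
| Bleach baths | No | No listed class title describes them, however they are recorded |
| Crisaborole, tar | No | Topicals that are not corticosteroids; no listed class title fits |
| TCI | Only if on the rescue CRF | No listed title names them; protocol 5.5.6 prohibits TCI use other than as rescue in sensitive areas |
| Systemic corticosteroids | No, by title | D07 is limited to dermatological preparations; L04 is titled immunosuppressants |
| Biologics, JAK inhibitors | Cannot be settled | L04 with COMD3 may reach them; COMD3 is not defined in the documents |

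Non-drug therapies are coded in a different dictionary. SAP 2.4.2 says: "Medical procedures and significant non-drug therapies as coded in MedDRA will be summarized along with medications". An ATC search therefore cannot find them. On corticosteroids, SAP 2.3.2 has its own baseline line, "Previous exposure to systemic corticosteroids(yes, no", separate from immunosuppressant therapy. That supports the reading by title but does not prove how records are coded.

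**Step 2. Does another rule catch the patient?**

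- Discontinuation: Table 5-1 keeps users of the topical treatments, phototherapy and bleach baths on study treatment. It does the same for systemic immunosuppressives unless the investigator sees a safety risk. The discontinuation rules in SAP 2.5.1 then do not apply.
- Adjudication: protocol 8.5 weighed type, indication, timing and frequency of medication, and was not tied to a class list. It has been dropped.
- Supportive estimands: 1 and 3 use the same confounding term, and 2 ignores confounding use. Estimands 1 and 2 treat discontinuation alike, so comparing them shows the effect of listed therapies only. A user of an unlisted therapy is handled identically in both.

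**Step 3. One patient traced (assumed case)**

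Baseline IGA is 3, phototherapy is given at Week 13, study drug continues, and Week 16 IGA is 1. There is no rescue CRF entry and no D07, R06A or L04 record, so the patient is not confounded. The score is 1 and the improvement is 3 − 1 = 2 points. The result is a responder.

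**Step 4. Size per patient**

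Inputs: planned arms of 90 (placebo, 30 mg, 50 mg) and 45 (3 mg, 10 mg), and an assumed placebo rate of 10% (protocol 9.8). The shift from one misclassified patient is 1/n.

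- n = 90: 1/90 = 1.1 percentage points
- n = 45: 1/45 = 2.2 percentage points

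At 10%, a placebo arm of 90 has 0.10 × 90 = 9 expected responders; one false responder makes it 10/90 = 11.1%. The number of users is not given. As an assumed range, 0 to 2 misclassified patients in an arm of 90 gives 0 to 2/90 = 2.2 points. If equal proportions are misclassified in two arms, their difference does not move.

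**The case against.** The case on the other side is substantial.

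- **Practical effect.** The trial stopped for lack of efficacy and MCP-Mod was dropped. The SAP states in 2.5.1 and section 4 that the way confounding use was handled made no difference to the interim conclusions. This stands as a limit on impact. It does not repair the definition: the statement concerns interim data, and the SAP does not say that the unlisted therapies were examined.
- **The usual route is covered.** Permitted rescue, including TCI in sensitive areas, is captured from the rescue CRF. A misclassified patient must use an unlisted therapy, stay on study drug and still meet the IGA criteria. This stands.
- **Class contents are not visible.** Table 5-1 files systemic corticosteroids under immunosuppressive treatments, and the documents show neither the drug dictionary nor the meaning of COMD3. The baseline categories in SAP 2.3.2 are not ATC mappings, and they separate biologics from immunosuppressants too. The gaps for systemic corticosteroids and TCI are therefore inferences from titles. Those for non-drug therapies, crisaborole and tar do not depend on this.
- **Direction.** A reader might infer that unlisted therapies are used more in poorly controlled arms, which would raise the placebo and low-dose rates and flatten the dose-response. The documents do not support this. They give no use by arm, and SAP section 4 reports no treatment effect at the interim. The SAP is also stricter than the protocol elsewhere: any rescue use is non-response without adjudication, and all R06A use counts. The net effect on any arm is unknown.

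**Conclusion.** The rule is wrong as written and should be corrected, but it is not shown to threaten the trial's conclusion. The list does not cover every AD-active row of Table 5-1, so it can classify as a responder a patient whom the SAP's general rule makes a non-responder. This is clear for phototherapy, tanning booths, bleach baths, crisaborole and tar. It is likely, by class title, for systemic corticosteroids and for TCI recorded outside the rescue CRF.

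The size is 1.1 points per patient at 90 per arm and 2.2 at 45, on the planned arm sizes. A reader might rescale this to the 187 patients in the interim analysis. That is the interim count; for the final sample the SAP says only that it is below 360, so no final per-arm figure can be given. The number of users may be zero. Nor do the documents support reading this gap as an explanation for the lack of efficacy.

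**What to change.** Before database lock, and without reference to treatment, map each AD-active row of Table 5-1 to medication terms, routes or procedure codes. Then revise the list in SAP 2.1.1:

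- add systemic corticosteroids, identified by route;
- add TCI found in the concomitant medication data;
- add other topical AD treatments, including crisaborole and tar;
- add phototherapy, tanning booths and bleach baths from the procedures and non-drug therapy data;
- check that the biologics and JAK inhibitors named in Table 5-1 are reached by L04 with COMD3, and add any that are not.

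If a row is left out on purpose, give the reason. Record the narrowing or its correction in SAP section 4.

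The cost is small. Protocol 5.5.7 already requires medications, procedures and significant non-drug therapies to be recorded in the CRF, and the SAP is dated before database lock. The work is one further search, some coding and a paragraph of SAP text. Some response rates may come out slightly lower.
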